5 CONSENT

The participant must personally sign and date the latest approved version of the Informed Consent form before any of the study specific procedures are performed.

Written versions of the Participant Information and Informed Consent will be presented to the participants detailing the exact nature of the study, what it will involve for the participant, the implications and constraints of the protocol and any risks involved in taking part. It will be clearly stated that the participant is free to withdraw from the study at any time for any reason without prejudice to future care, and with no obligation to give the reason for withdrawal.

If he/she wishes to consider the information, the participant will be allowed as much time as he/she needs. He/she will be offered sufficient opportunity to question the Investigator, GP or other independent parties to decide whether he/she will participate in the study. Participants will not be rushed into making a decision. However, the convenience of the participant will also be considered including the right to immediate consent.

Written Informed Consent will then be obtained by means of participant dated signature and dated signature of the person who presented and obtained the Informed Consent. A member of the research team will go through the written information with the potential participant giving the opportunity for questions to be asked. Only researchers experienced in consent procedure and trained in Good Clinical Practice will take consent from participants.

In gaining consent from the participant we will ensure that the participant is able to:

1. Understand the purpose and nature of the research
2. Understand what the research involves including potential benefits and burden
3. Understand that the alternative to taking part is for them to receive standard medical care and that this is not affected by participation
4. Retain information long enough to make an effective decision
5. Make a free choice

The original signed form will be retained at the study site.

If there is any further safety information that may result in significant changes in the risk/benefit analysis, the PIS and Informed Consent Form (ICF) will be reviewed and updated accordingly. All

participants that are actively enrolled on the study will be informed of the updated information and given a revised copy of the PIS/ICF in order to confirm their wish to continue on the study.

Non-English speakers will be offered the opportunity to participate with a translator if available.

6 ELIGIBILITY CRITERIA

Each participant must meet all the inclusion criteria, and none of the exclusion criteria, at entry to the study. Those who are ineligible or decline to participate will be captured on the secure and encrypted recruitment and screening log.

6.1 Inclusion Criteria

- Is 18 years of age or older
- Is willing to complete all study procedures
- Study A: Patients undergoing formal nuclear medicine (99mTc-DTPA) glomerular filtration rate testing or willing to have a venous GFR filtration panel (Study A only)
- Study B: Has Chronic Kidney disease (CKD) KDIGO criteria or is at risk of CKD due to heart disease or diabetes as determined by physician

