3 STUDY DESIGN

Study A: Cross-sectional cohort study

Study B: Observational longitudinal cohort study

Research Ethics Committee approval and R&I approval will be sought for the study. Participants who meet the entry criteria will be recruited and consented by the investigator, or any GCP qualified member of the local research team who has delegated responsibility for study recruitment. Participants will be recruited from King's College Hospital, Royal London Hospital outpatients and wards and nuclear medicine department. Participants will be offered a minimum of 24 hours to reflect on the patient information sheet (PIS), which will be provided during initial discussion. Participants will be selected purposively to include a range of age, gender, ethnicity (at least 50% African/Afro Caribbean), severity of renal disease and clinical settings. Participants in study A will be able to participate in study B if they wish to do so.

Demographics, Body mass index, waist circumference and lean body mass (Fresenius - Body Composition Monitor and clinician estimated), mobility at home, mode of transportation to come to hospital, length and cost of travel, carer details, drug history, number of hospital visits and GP visits per year and reason for laboratory creatinine testing (e.g. monitoring Ig A nephropathy) will be recorded. Data will be transferred following pseudo-anonymisation into a study specific database by the research team.

POC-Cr testing

Capillary POC-Creatinine concentration will be assessed by NovaMaxCreat (NovaBio) and Epoc (Siemens) POC hand-held devices. A quality control will be performed for each POC-Cr device each day by the study nurse and by participants, ensuring the reagent batch conforms the manufacturers' quality specifications. POC reagents will be stored and used following manufacturers' specifications.

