6.2 Exclusion Criteria

- Unable or unwilling to give informed consent
- Any condition which would make finger prick contraindicated e.g. severe skin conditions, bleeding disorder
- Study A: If formal GFR testing has been requested only because estimated GFR is not considered to reflect true GFR (e.g. liver disease)

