7 RECRUITMENT

Patients who meet the entry criteria may be recruited and consented by the investigator, or any GCP qualified member of the local study team who has delegated responsibility for the study. Participants will be recruited from King's College Hospital, Royal London Renal Units and Nuclear Medicine Departments. Potential participants will be identified when presenting for their routine hospital clinic visits or during an inpatient admission. Members of the site staff will pre-screen and screen for potential eligible study participants using the inclusion/exclusion criteria.

Screening logs will be kept on the secure renal research study hard drive and will be encrypted for confidentiality. All eligible and ineligible patients, plus those declining to participate will be logged on the secure screening log. Patients who fulfil the inclusion criteria will have their eligibility confirmed by the research team. After confirming eligibility, eligible patients will be approached by an appropriately trained member of the clinic team to ascertain interest in entering the study. This individual will give a comprehensive verbal explanation of the study. Time for questions throughout the discussion will be given and questions adequately addressed. Potential participants will be given enough time to reflect on the patient information sheet (PIS), which will be provided during the initial discussion with the patient.

If the participant is willing to take part then they will be asked to sign the consent form with a member of the research team countersigning. A copy of the consent form will be given to the participant, and an electronic copy will be filed securely with the participant's records.

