Accuracy of self-monitoring for the first and last reading taken by the participant will be assessed as outlined in Study A. Total, between-day, and within-day precision will be evaluated by comparing up to four POC-Cr capillary concentrations for seven days and compared to day 1 and 8 venous serum creatinine concentrations. Mean and standard deviation for each time point during the week, and within the day will be compared by an independent means *t*-test and *F*-test, respectively, using Stata Version 21 or greater. A *p*-value of less than 0.05 will be considered significant.

SUTAQ scale scores, relationships between scales and group differences on scales will be reported and compared with demographics, frequency, success and accuracy of testing.

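### Study B does not exclude maintenance dialysis, so a true creatinine cycle could be counted as imprecision of the self-test

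*Protocol*

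**What the plan says.** Entry to Study B (Protocol 6.1) is open to adults under this rule: "Study B: Has Chronic Kidney disease (CKD) KDIGO criteria or is at risk of CKD", the risk being one that a physician attributes to diabetes or heart disease. There is no upper CKD stage and no condition on stability.

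Two of the exclusions in section 6.2 apply to Study B. One concerns consent. The other is "Any condition which would make finger prick contraindicated e.g. severe skin conditions, bleeding disorder". The only kidney-related exclusion is labelled for the other study: "Study A: If formal GFR testing has been requested only because estimated GFR is not considered to reflect true GFR".

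On recruitment, section 3 selects purposively for a range that includes "severity of renal disease and clinical settings". Section 7 states: "Participants will be recruited from King's College Hospital, Royal London Renal Units and Nuclear Medicine Departments". It adds: "Potential participants will be identified when presenting for their routine hospital clinic visits or during an inpatient admission". Section 4, by contrast, has Study B participants approached in outpatients.

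On analysis, section 8 states for Study B: "Total, between-day, and within-day precision will be evaluated by comparing up to four POC-Cr capillary concentrations for seven days". These readings are set against venous creatinine on Days 1 and 8. Means and standard deviations by time point are compared with a t-test and an F-test. The schedule in section 4 collects medical history on Day 1 and reviews medication on Day 1 and at the final visit. No stated rule uses either to decide who enters the precision analysis.

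**The concern.** Repeated readings measure the precision of a device only when the quantity being measured stays about the same. In a patient on intermittent dialysis it does not: creatinine falls at each session and rises until the next. The spread of that patient's 28 readings would be mostly true change, yet section 8 would report it as imprecision.

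The two venous samples do not protect against this. They can show a net change from the start to the end of the week, but not a cycle within it. With sessions on fixed weekdays, the nominal Day 8 falls at the same point of the cycle as Day 1. The two venous values could then agree while creatinine moved widely in between.

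The stake is the use to which Study B is put. Section 1 says that self-monitoring depends on understanding how much one patient's capillary results vary. An estimate of ordinary variation that is inflated by dialysis cycles would make the self-test look less repeatable than it is. Anyone who used it to judge readings in non-dialysis CKD would discount changes that are real.

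**Working it through.** **Inputs from the Protocol.** Study B target: at least 40 (Study Summary). Readings per participant: 4 a day × 7 days = 28 (section 8). The Protocol gives no CV, standard deviation or precision target for Study B, so there is no figure of its own to reproduce.

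**Assumptions, not in the documents.** Stable within-person CV of 6%. For a dialysis participant, creatinine rises 9 µmol/L per hour, three 4-hour sessions a week each remove 50% to 65%, and readings are taken at 07, 12, 18 and 22 h.

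**Step 1: true CV on dialysis.** I ran this model to a steady weekly cycle for five session start times between 07:30 and 17:00. With 65% removal the CV of the 28 true values was 28% to 32%. With 50% removal it was 19% to 22%. I use 31% and 20% as the two ends. Most of the variation fell in the within-day component; how much reached the between-day component depended on the hour of the session.

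**Step 2: pooled within-person CV.** With k of 40 participants on dialysis and true dialysis CV equal to D,

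pooled CV = √[((40 − k)·6² + k·(6² + D²)) / 40] = √(36 + k·D²/40).

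| k of 40 | D = 20% | D = 31% |
|---|---|---|
| 0 | 6.0% | 6.0% |
| 1 | √(36 + 10.0) = 6.8% | √(36 + 24.0) = 7.8% (unrounded 7.75) |
| 2 | √(36 + 20.0) = 7.5% | √(36 + 48.1) = 9.2% |
| 4 | √(36 + 40.0) = 8.7% | √(36 + 96.1) = 11.5% |

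**Step 3: a second model.** This one assumes a device CV of 5% and a linear sawtooth with a 60% fall per session. A dialysis participant's observed CV is then 25.4%. With 2 of 40, pooled CV = √[(38·5² + 2·25.4²)/40] = 7.5%. With 4 of 40, √[(36·5² + 4·25.4²)/40] = 9.3%. The starting value is 5.0%, so direction and size agree with Step 2.

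**Step 4: drift instead of dialysis.** A steady 30% rise over the week adds a true CV of about 8%. With 4 of 40 such participants, pooled CV = √(36 + 4·8²/40) = √42.4 = 6.5%. That is small beside the dialysis effect.

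**The case against.** **Dialysis is never named as a route into Study B.** This stands as a limit on the point. The text admits such patients by silence, and the background describes self-monitoring as suited to early CKD. A reader might infer that Study B will enrol dialysis patients; the documents do not show that, or how many. Outpatient recruitment under section 4 weakens the route through acute illness, but it does not rule out maintenance dialysis.

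**Changing kidney function and drug changes.** A reader might extend the point to these. Step 4 does not support that for modest drift.

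**The 8.87% limit.** A reader might set the pooled CVs against this figure and conclude that the device would fail. Section 8 gives 8.87% as an allowable total error against a reference standard. It sets no pass mark for precision, so that comparison tests nothing in the plan.

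**The pooled CV is a choice made here.** True: section 8 describes means and standard deviations by time point, and the pooling method may properly sit in an SAP. The pooled figure only shows scale. The protocol does, however, own eligibility, and it states the precision analysis without any restriction.

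**Accuracy is mostly safe.** This stands. The hospital self-test has a simultaneous laboratory sample, so a true swing largely cancels in the paired comparison. What remains exposed is precision, and the comparison of serial readings with a single venous value, which section 2.1 lists as a primary objective of Study B.

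**Some biological variation is wanted.** Section 1 does seek variability within patients. But the stated analysis does not separate device error from true change, so calling the result precision misdescribes it.

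**Conclusion.** The point holds in a conditional form. As written, Study B does not exclude maintenance dialysis, and section 8 would count a dialysis participant's true creatinine cycle as imprecision. If 2 to 4 of 40 participants were on dialysis, the pooled within-person CV would rise by roughly a quarter to nine-tenths (6.0% to between 7.5% and 11.5%). That size rests on the assumed 6% stable CV, a true dialysis CV of 20% to 31%, and an enrolment share that the documents do not give; with no such participants the effect is nil. It is worth correcting because the change is small and the affected quantity is central to Study B. It is no ground for doubting the paired accuracy results.

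**What to change.** Choose one of two changes:

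- add maintenance dialysis to the Study B exclusions in section 6.2; or
- state in section 8 that the precision analysis is restricted to participants not on dialysis, with dialysis participants reported separately and kept for feasibility, safety and acceptability.

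Medical history is already taken on Day 1, so neither change needs new data collection beyond making sure that dialysis status is recorded.

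As a sensitivity analysis only, repeat the precision analysis without participants who have a relevant drug change or a marked venous change between Day 1 and Day 8. This should not be the main rule: it cannot see a cycle within the week, and it selects participants on a result obtained after entry.

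Reconcile section 4 (Study B approached in outpatients) with section 7 (identification during inpatient admissions, not limited to Study A).

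The cost is one line of text, the possible loss of a few participants from the precision analysis, and a precision result that applies to non-dialysis CKD.

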6.2 Exclusion Criteria

- Unable or unwilling to give informed consent
- Any condition which would make finger prick contraindicated e.g. severe skin conditions, bleeding disorder
- Study A: If formal GFR testing has been requested only because estimated GFR is not considered to reflect true GFR (e.g. liver disease)

7 RECRUITMENT

Patients who meet the entry criteria may be recruited and consented by the investigator, or any GCP qualified member of the local study team who has delegated responsibility for the study. Participants will be recruited from King's College Hospital, Royal London Renal Units and Nuclear Medicine Departments. Potential participants will be identified when presenting for their routine hospital clinic visits or during an inpatient admission. Members of the site staff will pre-screen and screen for potential eligible study participants using the inclusion/exclusion criteria.

Screening logs will be kept on the secure renal research study hard drive and will be encrypted for confidentiality. All eligible and ineligible patients, plus those declining to participate will be logged on the secure screening log. Patients who fulfil the inclusion criteria will have their eligibility confirmed by the research team. After confirming eligibility, eligible patients will be approached by an appropriately trained member of the clinic team to ascertain interest in entering the study. This individual will give a comprehensive verbal explanation of the study. Time for questions throughout the discussion will be given and questions adequately addressed. Potential participants will be given enough time to reflect on the patient information sheet (PIS), which will be provided during the initial discussion with the patient.

If the participant is willing to take part then they will be asked to sign the consent form with a member of the research team countersigning. A copy of the consent form will be given to the participant, and an electronic copy will be filed securely with the participant's records.

8 STATISTICAL METHODS

Study A: Readings taken with measured with NovamaxCreat and Epoc blood analysis system will be analysed separately. Bland-Altman plots and Passing-Bablok regressions will be generated for POC-Cr concentrations using Stata version 21 or later. The analytical error percentage compared to the reference standards (IDMS enzymatic traceable and 99mTc-DTPA and GFR filtration panel) ($=100 \times ([\text{POC device}] - [\text{reference standard}]) / [\text{reference standard}]$) will be calculated for each POC-Cr recording in each participant. In addition, average analytical error percentage and a 95% confidence interval (95%CI) will be calculated following Clinical Laboratory Standards Institute procedures.¹⁶ Criteria used to check analytical error percentage will be derived from the 'Desirable Specifications for Allowable Total Error (ATE)' database for creatinine (ATE=8,87%)¹⁵ and from the Laboratory Working Group of the National Kidney Disease Education Program (NKDEP) for eGFR (ATE=10%)¹⁷. Although the 10% ATE for eGFR is actually a performance specification for creatinine, it has been used in as an acceptable total error for eGFR.^{18,19,20} Categorical agreement of POC-Cr concentrations with the reference standards will be calculated using the unweighted Kappa statistic. Error analysis using predefined minor and major classification errors will be performed for POC-Cr concentrations. POC-Cr concentrations and reference standards will also be assessed by Deming regression and Pearson's correlation coefficient. Bias offset required will be recorded

Proportion of patients correctly identified to have CKD $eGFR < 60 \text{mls/min/1.73m}^2$ will be reported. Sensitivity and Specificity of different Cr thresholds calculated.

Study B: Number of tests attempted per participant, daily frequency of testing and proportion of successful attempts will be reported. Reasons for unsuccessful attempts and adverse events will be described and quantified if appropriate. Time taken to train per patient will be reported in minutes as median and IQR.

Accuracy of self-monitoring for the first and last reading taken by the participant will be assessed as outlined in Study A. Total, between-day, and within-day precision will be evaluated by comparing up to four POC-Cr capillary concentrations for seven days and compared to day 1 and 8 venous serum creatinine concentrations. Mean and standard deviation for each time point during the week, and within the day will be compared by an independent means *t*-test and *F*-test, respectively, using Stata Version 21 or greater. A *p*-value of less than 0.05 will be considered significant.

SUTAQ scale scores, relationships between scales and group differences on scales will be reported and compared with demographics, frequency, success and accuracy of testing.

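### Section 8 reads as Bland-Altman analysis in concentration units while its accuracy limits are percentages; add percentage-scale limits of agreement and the share of readings within 8.87%

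*Protocol*

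**What the plan says.** Protocol section 8 states, for Study A, that "Bland-Altman plots and Passing-Bablok regressions will be generated for POC-Cr concentrations". Later in the same paragraph it adds that "POC-Cr concentrations and reference standards will also be assessed by Deming regression and Pearson's correlation coefficient". It does not say whether the Bland-Altman differences are absolute, percentage or log differences. It does not mention limits of agreement, and it does not say whether the Deming regression is weighted.

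The same paragraph defines a percentage error, 100 × (device − reference) / reference, which "will be calculated for each POC-Cr recording in each participant". It then says that "average analytical error percentage and a 95% confidence interval (95%CI) will be calculated". This percentage error is what is checked against the allowable total error of 8.87% for creatinine and 10% for eGFR.

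Section 3 selects participants purposively over a range that includes "severity of renal disease and clinical settings". Section 8 also assesses the accuracy of the first and last self-tests in Study B by the Study A methods, so the choice of scale carries over to Study B.

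**The concern.** A percentage tolerance allows a larger absolute error at a higher creatinine. A single pair of Bland-Altman limits in umol/L describes the same absolute error at every level. The two agree only if creatinine varies little or if device error does not grow with concentration. The sampling plan makes a narrow creatinine range unlikely.

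Bland-Altman analysis is the named method that would normally show how far one finger-prick result can lie from the laboratory value. If error is roughly proportional, raw limits are driven by the high-creatinine participants. The device would then look worse than it is at low creatinine and better than it is in advanced disease. The mean percentage error with its CI cannot make up for this, because positive and negative errors cancel in a mean. Individual scatter is also relevant to the section 2.2 objective of defining a range of readings that need confirmation.

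**Working it through.** The protocol states no limits of agreement, SD or device CV, so there is no figure to reproduce. What follows shows the consequence under stated assumptions.

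**Inputs from the protocol:** creatinine limit 8.87%; Study A n = 375.

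**Assumed inputs:** true creatinine lognormal with median m = 120 umol/L and geometric SD 1.8 (log-SD s = ln 1.8 = 0.588); proportional device error with CV 8%; laboratory CV 2%; no systematic bias.

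**1. True relative spread.** t = √(0.08² + 0.02²) = 0.0825. The 95% spread is 1.96 × 0.0825 = ±16.2% at every level.

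**2. Raw limits.** The SD of the differences is t·√E(x²) = t·m·exp(s²) = 0.0825 × 120 × 1.413 = 13.98 umol/L. The limits are ±1.96 × 13.98 = ±27.4 umol/L.

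| Creatinine, umol/L | Raw limits as % | True 95% spread |
|---|---|---|
| 80 | 34% | 16% |
| 110 | 25% | 16% |
| 400 | 7% | 16% |

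The raw limits are right only at m·exp(s²) = 120 × 1.413 ≈ 170 umol/L. Simulation with creatinine clipped to 40–900 umol/L gives coverage of the nominal 95% limits of about 100% below 100 umol/L and 76% above 200.

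**3. Range.** Over geometric SD 1.5 to 2.2 and CV 6 to 12%, the limits at 80 umol/L are 1.8 to 2.7 times too wide, and coverage above 200 is 74 to 80%. A second grid (median 110 or 150, log-SD 0.3 to 0.7, CV 4.5 to 15%) gives coverage of 98 to 100% at 100 umol/L and 44 to 77% at 400.

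**4. What the mean hides.** In the base case the mean percentage error is about 0%. The share of readings within 8.87% is P(|Z| < 8.87/8.25 = 1.076) = 72%. At device CV 15% the mean is still about 0%, and the share is P(|Z| < 8.87/15.13 = 0.586) = 44%.

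**5. If error is not purely proportional.** Take a constant error SD of 5 to 10 umol/L plus a 5 to 6% proportional part, with the same creatinine distribution. Raw limits at 80 umol/L are then 1.2 to 1.7 times too wide and cover 79 to 85% above 200. Percentage limits also fit imperfectly: they cover 86 to 90% below 100 umol/L and 99 to 100% above 200. Neither scale is right everywhere.

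**6. Deming regression** (n = 375, median 110, log-SD 0.5, CV 10%). The SD of the estimated bias at 100 umol/L is 0.61 unweighted against 0.53 weighted; at 400 it is 6.5 against 3.7. Mean bias at 100 is about −0.5 umol/L for both. In the scenario with the largest bias (median 150, log-SD 0.3, CV 15%), mean bias at 100 is −7.7 unweighted and −6.6 weighted. Most of that comes from taking the error-variance ratio as 1, not from omitting weights. The effect of weighting is mainly on precision.

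**The case against.** The strongest reply is that the protocol never commits to raw-unit limits. The word concentrations names what is measured, and a percentage Bland-Altman plot is also a plot of concentrations. Difference scale and Deming weights are details often left to an analysis plan, which may exist. This stands in part: raw units and unweighted Deming are the plain reading, not a stated rule. A reader might infer that the protocol prescribes raw limits and therefore misstates agreement. The text does not go that far.

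A reader might also infer that the accuracy verdict or the eGFR 60 decision is compromised. The documents do not support that. The percentage error is calculated for every reading, and it, not the Bland-Altman plot, is compared with 8.87% and 10%. The eGFR 60 question is handled by the proportion correctly identified and by sensitivity and specificity, with kappa and classification errors for categorical agreement. None of these uses limits of agreement. In Study A, comparing device with serum creatinine is itself a secondary objective (section 2.2).

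Third, a percentage tolerance is a performance specification and says nothing about how this device's error behaves. That is correct, and step 5 shows that percentage limits can also fit poorly. It argues for reporting both scales and checking by band, rather than replacing one with the other.

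On Deming regression the objection largely holds. The effect is mainly lost precision, and Passing-Bablok regression, also planned, does not need constant error variance.

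What the objection does not remove is that individual percentage errors have no named summary beyond their mean and CI.

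**Conclusion.** The point holds as a low-cost improvement to section 8, not as a demonstrated error. On its plain reading, the plan shows individual agreement in concentration units, judges accuracy in percent, and summarises percentage error only by a mean with CI.

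If error grows with concentration, one raw band would be about twice too wide at 80 umol/L and would cover roughly three quarters of readings above 200 (base case; 1.8 to 2.7 times and 74 to 80% over the range tried). A mean error near 0% could coexist with 72% of readings, or fewer, inside the plan's own 8.87% limit. These sizes rest on an error structure, device CV and creatinine distribution that the protocol does not give. With a substantial constant error component the raw-scale problem is smaller, and percentage limits under-cover at low creatinine.

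**What to change.** In section 8, state that:

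- Bland-Altman bias and 95% limits of agreement will be reported on percentage (or log-ratio) differences, alongside the raw-unit plot.
- The proportion of individual readings within 8.87% of the laboratory value will be reported for each device, in addition to the mean percentage error and its CI.
- The limits will be checked by creatinine band, because neither scale fits throughout if error has both constant and proportional parts.
- As a secondary refinement, Deming regression will be weighted when error is found to be proportional, with the assumed error-variance ratio stated.

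The cost is a few sentences and slightly more reporting. No new data or participants are needed. The planned percentage-error check, kappa, sensitivity and specificity stay as they are.
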